## **6.2 IMPORTANT PROTOCOL DEVIATIONS**

Listings of protocol deviations will be provided to be discussed at the MQRM, at the Trial Oversight Meeting prior to DBL or at the RPM. At these meetings, it will be determined whether a discrepant data value can be used in analyses or whether correction is needed. Each protocol deviation must be assessed to determine whether it is an important protocol deviation (iPD). Refer to the Integrated Quality and Risk Management Plan (IQRMP) Section 4.1 for the detailed specifications of PDs and iPDs (32). For the process of identification of iPDs, refer to "Identify and Manage Important Protocol Deviations (iPD) (3).

If any iPDs are identified, they are to be summarized into categories and will be captured in the MQRM/RPM minutes or the TOM minutes and additionally via an accompanying Excel spreadsheet. The iPDs may lead to exclusion of subjects from analysis sets (e.g., the Per Protocol Set), referring to IQRMP. The documentation of the iPD categories and how to handle iPDs in the analysis is included in the DV domain specifications and stored within the TMF in EDMS.

All COVID-19 related protocol deviations, regardless of important or non-important ones will be included in the DV domain as well. See *BI-KMED-COPS-HTG-0141* "CTR writing guidance for trials impacted by the COVID-19 pandemic" (31) and *BI-KMED-COPS-HTG-0117* "IQRM and Centralized Monitoring during COVID-19 - Guidance for Trial Teams" (33) for details.

A summary of iPD decisions will be documented in the decision log.

## **6.3 SUBJECT SETS ANALYSED**

The following analysis sets will be defined for the randomized maintenance treatment period of this trial:

- Enrolled Set (ES)  
This subject set includes all subjects who signed informed consent. It will be used to display the subject disposition.
- Randomized Set (RS):  
This subject set includes all randomized subjects. Treatment assignment will be used as randomized. It will be used for analyses of subject for baseline demographics and

disease characteristics and is the main set for the analyses of efficacy endpoints during the randomized maintenance treatment period.

- **Safety Analysis Set (SAF):**  
This subject set includes all subjects who were randomized and received at least one dose of study drug. This is the main analysis set for safety. Subjects will be analyzed according to the actual treatment received.
- **Per-Protocol Set (PPS):**  
This subject set includes all subjects in the randomized set who adhered to the CTP without any iPDs which are flagged for exclusion from the PPS. The PPS will be used for sensitivity analysis on the primary and key secondary endpoints.

For the flare treatment period, the following set is defined as below:

- **Safety Analysis set for flare treatment period (SAF-FT):**  
This subject set includes all subjects who took at least one flare treatment with OL i.v. dose of spesolimab. This is the main analysis set for efficacy and safety during the flare treatment period.

For the OL maintenance treatment period, the following set is defined as below:

- **Safety Analysis set for OL maintenance treatment period (SAF-MT):**  
This subject set includes all subjects who received at least one dose of OL s.c. maintenance treatment. This is the main analysis set for efficacy and safety during OL maintenance treatment period.

### **Handling of Treatment Misallocations in the Analysis Sets**

If a subject is randomized but not treated, they will be reported under their randomized treatment group for efficacy analysis according to RS and PPS (per the intent-to-treatment principle). Such subjects are excluded from the safety analyses (SAF) since no randomized study medication was taken.

If a subject is treated but not randomized, they will be excluded from the efficacy analysis and safety analysis. However, subjects under such circumstances will be described in the final CTR.

If a subject is randomized but took incorrect treatment during the study,

- For efficacy analyses according to the RS and PPS, subjects who took incorrect treatment will be reported under their randomized treatment group.
  - In the case of stratification error at randomisation, the subjects will be analyzed according to the stratum to which they actually belong to (regardless of any mis-assignment to treatment based on identification of the wrong stratum from IRT), as such an error occurs before randomisation and is therefore consistent with regulatory guidance.

- For the safety analysis based on SAF, the actual treatment will be used as below:
  - For subjects randomized to active spesolimab arms and are planned to receive multiple dose administrations of spesolimab, in the case of incorrect medication taken, the subjects will still be reported under their randomized treatment group for safety analysis, as the overall safety profile is expected to be driven by the amount of spesolimab received in totality over the entire treatment duration. If the subject receives only a few syringes of the incorrect medication at only some dosing visits, it is not expected that the safety profile will deviate from the planned treatment regimen.
  - For subjects randomized to placebo: if the subject receives  $\geq 1$  syringe of randomized spesolimab s.c., they will be reported as treated under **Speso SC Low** dose group.

[figure not shown]
The discussion of all exceptional cases and the decisions on the allocation of subjects to populations will be made at the last the RPM/DBLM.

[figure not shown]
Table 6.3: 1 Subject sets analyzed

Class of endpoint	Subject Set					
	ES	RS	PPS	SAF	SAF-FT	SAF-MT
Disposition	X					
iPDs		X				
Demographic		X				
██████████				█	█	█
Baseline characteristics		X			X	
Primary endpoint		X a	X b			
Key secondary endpoint		X a	X b			
Secondary endpoints		X				
██████████		█			█	█
Adverse event				X	X	X
Lab/other safety/ tolerability				X	X	X

a Primary analysis

b Sensitivity analysis

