7.2 PLANNED ANALYSES

7.2.1 General considerations

There will be 3 main patient populations in this trial for analyses: the randomized set (RS), the safety set (SAF), and the per-protocol set (PPS).

Randomized Set

This patient set includes all randomized patients. Treatment assignment will be as randomized. This is the main analysis set for presentation of efficacy.

Safety Set

This patient set includes all patients who were randomized and received at least one dose of study drug. It will be the main analysis set for presentation of safety. Patients will be analyzed according to the actual treatment.

Per-Protocol Set

This patient set includes all patients in the RS who adhered to the CTP without any IPVs (potentially affecting the study outcome) which lead to exclusion from the PPS. This set will be used for sensitivity analysis on the primary and key secondary efficacy endpoints which are included in the testing hierarchy.

Important violations of the protocol will include violations of the key inclusion and exclusion criteria, incorrect medications taken, concomitant use of restricted medications, and any other violations of the protocol deemed important by the study team. All decisions concerning important protocol violations will be made prior to un-blinding of the database for the primary trial analysis.

Standard statistical parameters (number of non-missing values, mean, standard deviation (SD), median, quartiles, minimum and maximum) or frequency tables (including patient frequencies and percentages) will be calculated where appropriate.

A Clinical Trial Report will be prepared for the primary analysis.

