### **7.8.1 Adverse Events**

AEs will be coded with the most recent version of MedDRA. Subjects will be analyzed according to the actual treatment received in each treatment period, i.e., randomized maintenance period, flare treatment period and OL maintenance period, respectively. In addition, the analysis for overall period post use of any spesolimab (s.c. or i.v.) will be performed for all subjects received at least one dose of spesolimab (s.c. or i.v.).

The exposure adjusted incidence rate (per 100 subject years) of a treatment emergent adverse event (TEAE) is defined as the number of subjects experiencing the adverse event per treatment group during time at risk divided by the total time of subjects at risk in that treatment group to contribute the event to the analysis multiplied by 100 (per 100 subject years), where:

Time at risk [subject years] = (date of onset of TEAE – the first dose of treatment in the applicable treatment period + 1) / 365.25 for subjects with onset of TEAE

During randomized maintenance treatment period, if the selected treatment emergent adverse event did not occur, the time at risk will be censored at the end of the treatment period as defined in [Section 6.1](#).

To distinguish the GPP flare symptoms from treatment emergent adverse event, sensitivity analysis for the safety during randomized maintenance treatment period will be done by censoring the time at risk to 7 days prior to first spesolimab iv treatment for subject who received the rescue spesolimab i.v. treatment. For subjects without the flare treatment, the time at risk will be censored at the end of the randomized treatment period as specified in [Section 6.1](#).

For the randomized maintenance treatment period, analysis of the time to the first specific AE, which will be pre-defined in the ISS SAP, may also be provided. Kaplan-Meier (KM) estimates of the survival/failure probabilities, as well as the median time-to-event, will be displayed by randomized treatment arm. Confidence intervals will be based on two-sided  $\alpha=0.05$  using complementary log(-log) transformation (conftype=loglog). A Kaplan-Meier curve will also be produced. For subjects who do not experience the defined the event, the time at risk will be censored at the end of the treatment period as defined in [Section 6.1](#).

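### In the randomised-period safety tables, the SAP moves a placebo patient given one active syringe to the low-dose group with all earlier placebo data, but keeps misdosed active-arm patients as randomised with no stated limit.

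*SAP*

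**What the plan says.** Three places set the same principle for safety:

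- Protocol 7.2.1, Safety Set: "Patients will be analyzed according to the actual treatment".
- SAP 6.3, Safety Analysis Set: "Subjects will be analyzed according to the actual treatment received".
- SAP 7.8.1, adverse events: "Subjects will be analyzed according to the actual treatment received in each treatment period".

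None of them defines actual treatment. The SAP 6.3 subsection on treatment misallocations does so for the safety set, with a different rule for each kind of arm.

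- **Active arms:** "in the case of incorrect medication taken, the subjects will still be reported under their randomized treatment group for safety analysis". The reason given is that "the overall safety profile is expected to be driven by the amount of spesolimab received in totality over the entire treatment duration". The sentence after it describes a mild case, "If the subject receives only a few syringes of the incorrect medication at only some dosing visits", and expects no change in the safety profile there.
- **Placebo arm:** "For subjects randomized to placebo: if the subject receives" ≥1 "syringe of randomized spesolimab s.c., they will be reported as treated under" Speso SC Low.

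Exceptional cases, and the allocation of patients to populations, are left to the last review or database lock meeting (RPM/DBLM). No criterion is given for what is exceptional.

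**The concern.** The two rules rest on opposite reasoning. For the active arms, a wrong syringe is treated as unimportant because total exposure drives safety. For placebo, a single active syringe decides the patient's group for the whole randomised period.

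The placebo rule has a direct consequence. Adverse events that began before any spesolimab was given leave the placebo column and are reported as low-dose events. They also enter Speso SC Total, which SAP 6.1 uses for adverse events. The active-arm rule has the converse problem: read literally, a patient given a different regimen throughout stays in the randomised dose column. Evaluating the safety and tolerability of the s.c. doses is a trial objective (protocol 2.1.1), and these by-arm tables are where a reader will look for it.

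**Working it through.** **1. Planned totals (SAP Table 7.4:1), loading dose plus maintenance doses.**

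- Low: 300 + 3 × 150 = 750 mg
- Medium: 600 + 3 × 300 = 1500 mg
- High: 600 + 11 × 300 = 3900 mg

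All three match the SAP. Placebo is 0 mg. One active syringe holds 150 mg (protocol Table 4.1.1:1).

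**2. The placebo trigger against the SAP's own reasoning.** A placebo patient has 4 + 11 × 2 = 26 planned syringes (protocol Table 4.1.4:1). One active syringe among them is 1/26 = 3.8% of syringes and 150/750 = 20% of the low-dose total. The midpoint between placebo and low is 750/2 = 375 mg, or 2.5 syringes. By total amount received, a patient with one or two active syringes is nearer placebo than low dose, yet the rule moves that patient.

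**3. Timing.** SAP Table 6.1:1 starts the randomised phase at the first randomised dose (Day 1). SAP 7.8.1 counts time at risk from the first dose of the period. The misallocation rule does not limit the move to later data. For a placebo patient still on randomised treatment who is misdosed at week 44 (Day 309), 309 − 1 = 308 days precede any active drug. That is about 10 months, or 308/365.25 = 0.84 subject-years. It is close to the worst case, since week 44 is the last dosing visit.

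**4. The active-arm clause.** It carries no limit. Read alone, it keeps in Low a patient given the full high regimen (3900/750 = 5.2 times the plan), and also a patient given only placebo (0 mg). The SAP's total-amount reason would move both.

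**5. Size of one move.** With 30 patients per arm, one patient is 1/30 = 3.3%. The counts below are assumed for illustration; the documents give none. Suppose an event occurs in 4 placebo and 3 low-dose patients, and one placebo patient with the event is moved.

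| | Before | After |
|---|---|---|
| Placebo | 4/30 = 13.3% | 3/29 = 10.3% |
| Speso SC Low | 3/30 = 10.0% | 4/31 = 12.9% |

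With these counts the direction of the difference reverses.

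**6. The plan's handling of i.v. rescue.** Protocol 7.2.5 censors time at risk at rescue with spesolimab and takes later safety data out of the planned-treatment displays. Those data go into summaries of everything after any spesolimab use. SAP Table 6.1:1 ends the randomised phase one minute before rescue. So a placebo patient who receives 900 mg i.v. keeps the earlier events under placebo, while one who receives 150 mg s.c. by mistake does not.

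**The case against.** The best defence is that the misallocation subsection is itself the working definition of actual treatment. The protocol leaves the term open, and SAP section 3 describes the SAP as a more detailed elaboration of the protocol. SAP section 4, where changes would be declared, is partly redacted. This stands to the extent that an undeclared change cannot be alleged. It does not help the placebo rule, because data from before any active drug are not low-dose data under any definition of treatment received.

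The asymmetry also has a rationale. A wrong dose within the active arms changes the amount of drug, whereas active drug in a placebo patient changes unexposed to exposed. Keeping exposed patients out of the comparator is reasonable. A split at the first active syringe achieves that without relabelling unexposed time.

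A reader might infer that active-arm patients stay in their randomised group whatever they received. The documents do not go that far. The stated reason covers only a few syringes at some visits, and the exceptional-case provision could catch a patient on the wrong regimen throughout. What is missing is the criterion. Gross errors are also unlikely, because the IRT assigns a numbered syringe at each visit and dosing is supervised.

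Two other strong readings fail. The rule does not govern all safety data: the flare and open-label periods have their own sets and labels. Nor is a comparison of safety between doses a stated objective; safety is descriptive, with no hypothesis test.

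Finally, the Overall Speso summaries already cover the period after any spesolimab use, and individual data are listed. Misdosed patients are therefore not hidden, but the by-arm columns stay as described.

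**Conclusion.** The concern holds for safety-set data of the randomised period. The placebo rule is the firmer part: followed as written, it puts placebo events and time at risk into the low-dose column. The active-arm rule is an as-randomised rule under an as-treated label, with no stated limit and an exception that has no criterion.

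The practical effect is probably small. It depends on the number of misallocations, which the documents do not give, and is confined to descriptive safety tables. Efficacy on the randomised set is unaffected. A broader conclusion, that the trial's safety is not analysed by actual treatment, is not supported. The correction is cheap and worth making before unblinding.

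**What to change.** Replace the two safety bullets in the SAP 6.3 misallocation subsection.

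- **Placebo patients given any active syringe:** keep events and time at risk before the first active syringe under placebo, and censor there, as the plan does at i.v. rescue. Report later data under active exposure: Overall Speso, and Speso SC Low as well if wanted. An event starting on the day of that syringe goes to the active side, in line with the SAP 7.8 convention for the first dose of a period.
- **Active-arm patients:** keep the randomised group when only isolated syringes differ. Otherwise assign the group by total spesolimab received against the planned totals of 0, 750, 1500 and 3900 mg. A nearest-total rule gives the threshold. Between low and medium the midpoint is (750 + 1500)/2 = 1125 mg, so a low-arm patient moves only after three or more extra active syringes, since (1125 − 750)/150 = 2.5. For patients who stop early, compare with each arm's planned total up to the same visit. Otherwise a correctly dosed high-arm patient stopping after week 8, with 600 + 2 × 300 = 1200 mg, would look like a medium-dose patient.
- **All arms:** list every misdosed patient, with syringes received and dates.

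A rule based on what was given at most visits should not be used. Correctly dosed low and medium patients receive placebo only at 8 of 12 dosing visits (protocol Table 4.1.4:1), so it cannot separate low, medium and placebo.

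The cost is one SAP paragraph, one variable derived from the syringe-level dispensing data, and slightly more programming. A misdosed placebo patient may appear in two columns, so column totals can exceed the number of patients and need a footnote.

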## **6.5 POOLING OF CENTRES**

This section is not applicable because centre/country is not included in the statistical model.

## **6.6 HANDLING OF MISSING DATA AND OUTLIERS**

Section 7.3 of the CTP describes the handling of missing data.

The original results (OR) approach implies the presentation of data exactly as observed (not using time windows and not setting values to missing).

OR analysis will be performed on parameters and endpoints, such as adverse event, concomitant medications, and the use of investigator-prescribed SoC, those are not collected based on visits and assignment to time windows will be not necessary. It is not meaningful to apply any imputation rule for the replacement of missing values either.

### **6.6.1 Withdrawals**

The reasons for withdrawal from treatment will be reported as indicated on the eCRF.

### **6.6.2 Efficacy data**

Based on the different reasons for subjects' data missing for different endpoints, various approaches will be used to assess the impact of missing data on the efficacy endpoints of this trial, depending upon the type of the endpoint and treatment period (See [Table 6.6.2.1](#)). Approaches to be applied are described below.

### 6.6.2.1 Randomized treatment period

#### **Time-to-event efficacy endpoints**

Per CTP Section 7.3,

*It is generally assumed that given the severity of a GPP flare, patients will always report to the investigator in a timely manner in order to ensure that proper treatment is received so that the developing flare can be rapidly treated. For the primary endpoint, only observed GPP flare events will be included in the primary analysis. No further imputation will be implemented on the missing values of GPPGA score and/or missing GPPGA pustule sub score. This will be the primary imputation method for the primary analysis. The same imputation strategy will be used for the two secondary endpoints, time to first worsening of PSS and time to first worsening of DLQI in the hierarchical testing procedure.*

The detailed rules as outlined in [Table 6.6.2:1](#) will be used as the primary method for handling censoring (Primary Method, abbreviated to **PM**).

Note here, with no event confirmed, censoring will be made at the earliest of the date of End of Study, Day 351 and the occurrent date of intercurrent events which hypothetical approach applied (per [Table 5.1:1](#)). This will also be done even if a subject had an event afterwards. Day 351 is the last day of the analysis time window of week 48 per [Table 6.7:1](#). The details about analysis time windows can be found in [Section 6.7](#). Such specifications reflect the objective of the trial that the treatment comparison for randomized subjects is made within 48-week study period per CTP Section 2.1.1.

Table 6.6.2: 1 Primary Method (PM): Description of censoring rules for primary endpoint, and two secondary endpoints

Situation	Outcome (event or censored)	Date of outcome
Without post randomisation assessment		
No event led by an intercurrent event	Censored	Date of randomisation, or the date of first dose, whichever comes later.
The first event led by an intercurrent event	Event	Date of the first event led by an intercurrent event
With post randomisation assessment		
No event*	Censored	Earliest of last contact date on End of Study page, Day 351, censor date specified by Estimand (if applicable)
The first event*	Event	Date of the first event*

\*The event includes the event defined by endpoint and the event led by an intercurrent event per Estimand definition

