¹⁵EoS2 visit is applicable for patients who do not qualify or who do not agree to enter OLE trial (1368-0025) at Week 48. EoS2 is also applicable for patients who prematurely discontinue with the last dose of treatment after Day 232. Since these patients prematurely discontinued, they would not qualify to enter OLE trial.

¹⁶Skin biopsy is optional and is only to be done for patients who have consented for this procedure. V2 and V14 skin biopsies (optional): 1 lesional or non lesional (if no lesions are present) skin biopsy of 5 mm punch (split into half for IHC and RNASeq) should be collected prior to study drug administration.

¹⁸ Only applicable if infection testing was not done at V14/EoS1 visit.

¹⁹ Vital Status will be collected at V14 for patients who prematurely discontinue with the last dose of treatment up to and including Day 232 and who agree to be contacted further but do not agree for physical visits. See [Section 5.2.6.1](#) for further details.

²⁰ Vital Status will be collected at V15 for patients who prematurely discontinue with the last dose of treatment after Day 232 and who agree to be contacted further but do not agree for physical visits. See [Section 5.2.6.1](#) for further details.

²¹IRT registration is expected once at End of Study visit (as applicable) for a patient.

FLOW CHART 2 (GPP FLARE IV RESCUE)

	Flare confirmation	Rescue Treatment Period (i.v.)							Open Label Maintenance Treatment Period (s.c.)			Follow-up
Visit	F0	R1	R2	R3	R4	R5	R6	R7	V _x ¹³	V _{>x} ¹³	V14/EoS1 ¹⁴	EoS2 ¹⁵
Week*	0	1	1	1	2	3	4	8	12	Every 4 weeks prior to Week 48 of randomization per original maintenance treatment schedule in Flowchart 1	Week 48 of randomization per original maintenance treatment schedule in Flowchart 1	16 wks after last dose
Day relative to R1		1**	4	8	15	22	29	57	85			
Visit Window (days)					±3	±3	±3	±7	±3			
Criteria to receive rescue treatment		X										
Infection Testing											X	X ¹⁸
Physical examination ¹		X ^{C,T}	X ^T	X ^T	X ^T	X ^T	X ^T	X ^T	X ^T	X ^T	X ^T	X ^{C,T}
Vital signs ²		X	X	X	X	X	X	X	X	X	X	X
Fever Assessment ³	X	X										
Pregnancy test ⁴		X ^{U,(S)}		X ^{U,(S)21}					X ^{U,(S)}	X ^{U,(S)}	X ^{U,(S)}	X ^{U,(S)}
12 lead-ECG ⁵		X		X ²¹					X	X	X	X
Safety laboratory tests ⁶		X	X	X	X	X	X	X	X	X	X	X
Photographs of skin/skin lesions ⁷	X	X	X	X	X	X	X	X	X	X	X	X
Skin biopsies (optional) ⁸ – prior to dose		X					X				X	

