7.3 HANDLING OF MISSING DATA

Every effort will be made to collect complete data at all visits. However, missing data will still occur and approaches to handle this are proposed below.

It is generally assumed that given the severity of a GPP flare, patients will always report to the investigator in a timely manner in order to ensure that proper treatment is received so that the developing flare can be rapidly treated. For the primary endpoint, only observed GPP flare events will be included in the primary analysis. No further imputation will be implemented on the missing values of GPPGA score and/or missing GPPGA pustule subscore. This will be the primary imputation method for the primary analysis. The same imputation strategy will be used for the two secondary endpoints, time to first worsening of PSS and time to first worsening of DLQI in the hierarchical testing procedure. The detailed censoring rules as outlined in [Table 7.3: 1](#) will be used.

Table 7.3: 1 Primary Method: Description of censoring rules for primary endpoint, and two secondary endpoints in hierarchical testing procedure

Situation	Outcome (event or censored)	Date of outcome
Without post randomization assessment		
No use of rescue medication or investigator-prescribed SoC	Censored	Date of randomization
The first use of rescue medication or investigator-prescribed SoC	Event	Date of the first use of rescue medication or investigator-prescribed SoC whichever comes earlier
With post randomization assessment		
No event, and, no use of rescue medication or investigator-prescribed SoC	Censored	Date of last assessment with no event confirmed
The first event, or the first use of rescue medication or investigator-prescribed SoC	Event	Date of first event, or the date of first use of rescue medication or investigator-prescribed SoC whichever comes earlier

The sensitivity analysis (Sensitivity Method) will utilize different rules to deal with missing values in the above-defined endpoints. The alternative censoring rules for sensitivity analysis are defined in [Table 7.3: 2](#).

For the primary analysis of the key secondary endpoint:

Missing GPPGA or GPPGA pustule subscores will not be imputed and only observed values will be utilized. If a patient is followed up to Week 48 and there is no flare, use of rescue medication or investigator-prescribed SoC reported, then this patient will be considered as a responder (i.e., no flare event) for the key secondary endpoint.

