### **7.5.2 Secondary endpoint(s)**

The secondary endpoints defined below, for the secondary objective of the trial only, are included into the statistical testing strategy.

*Time to first worsening of Psoriasis Symptom Scale (PSS) up to week 48 defined as a 4-point increase in total score from baseline. Intake of rescue medication, or investigator-prescribed SoC, will be considered as onset of a worsening.*

*Time to first worsening of Dermatology Quality of Life Index (DLQI) up to week 48 defined as a 4-point increase in total score from baseline. Intake of rescue medication, or investigator-prescribed SoC, will be considered as onset of a worsening.*

The primary analyses of the two secondary endpoints are as same as that of the primary endpoint using **EM-PM** approach based on RS.

[figure not shown]
[figure not shown]
Subjects with the following situation/s will be censored at Day 1 in all corresponding time-to-event analyses

[figure not shown]
- Without a baseline evaluation in PSS/DLQI
- Do not eligible for the evaluation of worsening
  - PSS baseline >12;
  - DLQI baseline >26;
  - DLQI questionnaire for subject whose age is under 16.

[figure not shown]
The below-defined secondary endpoint is not included into the statistical testing strategy of the secondary objective.

*Sustained remission, defined as a subject with a GPPGA score of 0 or 1 (clear or almost clear) at all visits up to week 48, without intake of rescue medication, or investigator-prescribed SoC.*

[figure not shown]
The primary analysis of the above secondary endpoints is consistent with that of the key secondary endpoint using **EM-MI** approach.

[figure not shown]

[figure not shown]
[figure not shown]

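### For PSS and DLQI worsening, the SAP censors event-free patients at last contact or Day 351, the protocol at the last assessment; neither rule is unbiased, and the two need reconciling (minor)

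*SAP*

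**What the plan says.** **Protocol.** Table 7.3:1 (Section 7.3) is titled as a "Description of censoring rules for primary endpoint, and two secondary endpoints in hierarchical testing procedure", so it covers flare, PSS worsening and DLQI worsening. For a patient with a post-randomisation assessment, no event and no rescue or SoC, the censoring date is "Date of last assessment with no event confirmed".

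**SAP.** Table 6.6.2:1 (Section 6.6.2.1) covers the same three endpoints and gives, for the same patients, "Earliest of last contact date on End of Study page, Day 351, censor date specified by Estimand (if applicable". The note above it says that "with no event confirmed, censoring will be made at the earliest of the date of End of Study, Day 351" or the date of an intercurrent event handled hypothetically. For the primary estimand, the visible part of Table 5.1:1 counts rescue and SoC as events and applies treatment policy to other restricted medication. Nothing there censors, so the date is last contact or Day 351. SAP 7.5.2 makes this the primary analysis of PSS and DLQI worsening.

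**Reason given.** SAP 6.6.2.1 repeats the protocol's argument: "It is generally assumed that given the severity of a GPP flare, patients will always report to the investigator in a timely manner". The note supports the Day 351 cap by the 48-week objective.

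**The concern.** The prompt-reporting argument is about flares. It does not carry over to a questionnaire score. Rescue or SoC counts as a worsening (protocol 7.2.3), but a rise in score without such treatment is visible only when the form is completed. Under the last-contact rule, a patient who stops completing forms but remains in contact stays in the risk set and cannot have a score event.

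The protocol foresees contact without a score. Section 3.3.4.1 asks patients who refuse visits for safety information by phone. Flow Chart 1, footnote 19, reads "Vital Status will be collected at V14 for patients who prematurely discontinue with the last dose of treatment up to and including Day 232"; footnote 20 does the same at V15 for later last doses. V15 has no PSS or DLQI. Section 6.2 lets adolescents leave questionnaires uncompleted.

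PSS and DLQI are the third and fourth families of the formal hierarchy, and the low-dose tests receive alpha only after success on both (protocol 7.1). Two governing documents should not give different censoring dates for formally tested endpoints.

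**Working it through.** **1. The cap.** Planned Week 48 day: 48 × 7 + 1 = 337. With the +14-day analysis window, 337 + 14 = 351, as the SAP states.

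**2. Unassessed days per patient.** After Week 12, DLQI is scored only at Days 169, 253 and 337 (Flow Chart 1).
- Only the Week 48 DLQI missing, contact to Day 351: 351 − 253 = 98 days. With contact to Day 337: 84 days.
- Last dose and last DLQI at Day 253: V15 falls at 253 + 112 = Day 365, so the cap applies and the gap is again 98 days, if that contact sets the last contact date.
- One score at Day 29, contact to Day 337: 337 − 29 = 308 days.
- Week 48 score on the planned day: at most 351 − 337 = 14 days, so these patients hardly matter.

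**3. Effect on the analysis.** The documents give no rate for questionnaire loss or worsening, nor the share of worsenings that lead to rescue or SoC (below, the treated share). All of the following are assumptions:
- 30 per arm, unstratified log-rank, one-sided 0.0125 (illustrative).
- Worsening exponential at 10% per month (30.44 days), hazard ratio 1 or 0.4. True placebo probability by Day 337: 1 − exp(−0.10 × 337/30.44) = 66.9%.
- In the affected arm(s), 20% stop scoring at a uniform time unrelated to worsening but keep contact to Day 337.
- Patients with no post-baseline score are censored at Day 1 under both rules.
- 20,000 simulated trials per case.

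DLQI schedule, SAP rule vs protocol rule:

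| Case | 0% treated | 50% | 80% |
|---|---|---|---|
| Null rejection, loss in active only | 3.1% vs 1.3% | 1.8% vs 1.0% | 1.4% vs 0.7% |
| Null rejection, loss in placebo only | 0.5% vs 1.5% | 0.8% vs 1.7% | 1.2% vs 2.0% |
| Power, HR 0.4, loss in placebo only (about 60% with no loss) | 43% vs 57% | 53% vs 63% | 58% vs 67% |
| Placebo Kaplan-Meier, equal loss (true 66.9%) | 61.1% vs 66.9% | 64.3% vs 68.7% | 66.1% vs 69.7% |

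With equal loss, null rejection is 1.3–1.4% (SAP) vs 1.2–1.3% (protocol). A smaller repeat of 3,000 trials per case gave 2.5% for the protocol rule where the table shows 2.0%.

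PSS schedule: null with active-only loss 2.8% vs 1.2% (0% treated) and 1.8% vs 0.9% (50%); power with placebo-only loss 45% vs 58% and 54% vs 63%.

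Range, DLQI at 0% treated. Loss of 10% and 30%: null with active-only loss 2.1% vs 1.3% and 4.6% vs 1.2%; power with placebo-only loss 52% vs 59% and 35% vs 56%. Worsening of 5% and 20% per month: null 2.7% vs 1.3% and 3.3% vs 1.3%.

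**4. Why the protocol rule also errs.** It stops event-free patients at the last score but still counts rescue or SoC used later. Late follow-up is then kept only for patients who have an event, so worsening is overstated. Its Kaplan-Meier error becomes the larger one above a treated share of about 57–60%.

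**5. A third rule.** Stopping at the last score and not counting later rescue or SoC gave Kaplan-Meier 66.9–67.1% and null rejection 1.05–1.5% at every treated share from 0 to 100%.

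**6. Flares, for context.** Base placebo rates, equal 20% loss, true value 53.0%: SAP vs protocol rule 50.4% vs 53.0% if no later flare is detected, 52.5% vs 54.6% at 80% detection and 53.0% vs 55.0% at 100%. When most flares are reported, the SAP rule is the less biased one.

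**The case against.** The strongest reply is that the treated share is probably high. PSS and DLQI are tested only after success on the flare endpoints, and rescue itself counts as worsening. Comparing the assumed probabilities, 53.0/66.9 gives about 79% if flares lead to rescue or SoC. At 80% the SAP rule is closer to nominal and to the true Kaplan-Meier value than the protocol rule. In a check of 3,000 runs with base flare rates, all flares rescued, and score-only worsening of 1, 3 or 5% per month in both arms, power with no loss was 91/76/64%. With 20% active-only loss it was 92/81/70 (SAP) vs 90/74/61 (protocol); with placebo-only loss, 90/73/59 vs 93/80/68. Both rules are off by a few points, in opposite directions. This stands, and it rules out simply restoring the protocol rule. The 79% is an inference, however, not a figure in the plan.

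It also stands that the simulations keep every lost patient in contact to Day 337. A patient who withdraws has a last contact near the last visit, where the rules nearly agree. Section 3.3.4.1 asks for at least the Week 48 visit, and these endpoints are stated to be unpowered.

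Two stronger readings are not supported:
- **That the SAP contradicts itself.** A reader might set the last-contact row against the row for patients with no post-randomisation assessment ("Date of randomisation, or the date of first dose, whichever comes later"), or against SAP 7.5.2: "Subjects with the following situation/s will be censored at Day 1 in all corresponding time-to-event analyses". The former follows the protocol's own table. The latter concerns patients in whom worsening cannot be evaluated: no baseline, baseline too high, or under 16 for DLQI. Neither addresses follow-up that stops.
- **That the change is undeclared, or that no alternative analysis exists.** SAP Section 4 is partly redacted. Table 6.6.2:2, an alternative censoring rule for these endpoints, is not visible and may already be the protocol rule.

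**Conclusion.** A minor point that should be settled before unblinding. The two documents give different censoring dates for formally tested endpoints, and the stated argument for relying on observed events does not reach PSS and DLQI. Only patients without a Week 48 score who stay in contact are affected.

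Under the stated assumptions, equal loss leaves the test essentially unchanged and lowers Kaplan-Meier worsening by up to 66.9 − 61.1 = 5.8 points. One-arm loss moves the test either way, mainly at a low treated share. A reader might infer that the SAP rule inflates type I error outright. That needs loss mainly in the active arm, few worsenings treated and continued contact, and the documents establish none of these. A reader might also infer that the protocol rule is correct and more powerful. At 80% treated it rejects in 2.0–2.5% of null trials with placebo-only loss, against a nominal 1.25%, and gives Kaplan-Meier 69.7% against 66.9%. Its power above the no-loss value of about 60% is therefore partly bias.

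The third rule is near unbiased at every treated share, provided that questionnaire loss is unrelated to worsening. For flares, the last-contact rule is defensible under prompt reporting.

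**What to change.** 1. Split the event-free row of SAP Table 6.6.2:1 by endpoint, align the note above it (which says End of Study where the table says last contact), and reconcile both with protocol Table 7.3:1.
2. For PSS and DLQI, end follow-up at the last evaluable score of that questionnaire, no later than Day 351. Keep the existing Day 1 rules. Do not count rescue or SoC first used after that date.
3. Unless the redacted Table 6.6.2:2 already does so, report two sensitivity analyses: the protocol rule with later rescue or SoC counted, and the last-contact rule.
4. Report by arm how many patients have no Week 48 score, and the days from last score to last contact.
5. For flares, only reconcile protocol 7.2.2 and 7.3 with SAP 6.6.2.1.

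Cost: one table row, one or two sentences and a derivation, with no new data. Slightly less follow-up is counted. Late rescue and SoC events leave the primary PSS and DLQI analysis, which departs from the composite rule after the last score and must be stated. In some cases a few points of power are lost.
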